### 5.5 STRATEGIES FOR RECRUITMENT AND RETENTION

Participants will be enrolled at 12 obstetrical centers that are matched on demographics of patient population. Within each pair of centers, each will be randomly assigned to the CC or ECHO condition. We will enroll 264 women in total, half in each treatment condition.

Recruitment was impacted by the Covid-19 Pandemic, and we re-evaluated our recruitment plan based upon our first 16 months of recruitment (10.25.21). We reduced our anticipated sample size to 264 participants in total or 132 in each treatment group with an average of 20 participants per site, allowing for 10% attrition. For the engagement outcome, we anticipated screening 360 eligible patients.

Women will be enrolled at each site by a designated staff person (DSP), most likely a nurse (at the CC practices it will be the CM). We will be placing recruitment flyers and posters in the two clinic sites advertising the study. We will have a social media page that describes the project. A QR Code on the flyers and poster will direct potential participants to the social media page. There the woman can read about the study or choose to watch a short video describing the study. As recommended by ACOG,(33) the DSP will administer their standard opioid screening to all pregnant women at all sites. Women with a positive screen will be invited to participate. DSPs will then obtain written consent from patients who agree to participate in the trial or remote consenting will be done as described earlier. The DSM-5 checklist will be completed for the diagnosis of OUD. Women who meet criteria for OUD will be deemed eligible to participate in the trial. To minimize attrition, the DSP will then: 1) explain the importance of follow-ups, 2) rapidly schedule first visit with a provider associated with the study after confirmation of eligibility and consent, 3) collect at least 3 verified locators, 4) call women to remind them of their appointments, and will have contact with a significant other who can provide collateral information and maintain subject involvement. Investigators will monitor participants who drop out and explore with the staff reasons for the dropouts.

In addition to patient participants in the trial, qualitative interviews will be conducted with a subset of patient participants and physicians involved in the project. Patient participants will be contacted, consented and enrolled in this portion of the project by computer randomization.

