## 9.2 SAMPLE SIZE DETERMINATION

We plan to recruit a sample of 6 matched pair clusters (total of 12 clusters), with 6 clusters per condition and 20 patients per cluster for a total of 264 patients. Hypothesizing that CC will perform better than ECHO, this sample size achieves 80% power to detect a clinically meaningful minimum difference of 0.20 between the CC proportion (0.94) and the ECHO proportion (0.74).

To estimate the sample size needed to test differences between models of care in the proportion of women retained in treatment at delivery using a permutation test, we used the method of Hayes and Bennett (1999) for matched-pair cluster randomized trials. Our null hypothesis is  $p_{ECHO} = p_{CC}$  and the alternate hypothesis is  $p_{ECHO} \neq p_{CC}$ , where  $p$  is the proportion of women retained in treatment at delivery, setting a two-sided type 1 error rate of 0.05. We based the estimate of the proportion in the CC on a study by our co-investigator in which 94% of patients treated under a CC model continued MAT until delivery.

We could not find empirical data for an estimate of the coefficient of variation, so we followed the approach of Hayes and Bennett (1999). We generated 10,000 data sets with 6 clusters each, with true proportions assumed uniformly distributed between 0.72 and 0.99 to allow for a relatively wide range of plausible retention proportion values. In each of the simulated data sets coefficient of variation values were calculated based on formula (9) in the manuscript. This follows the conservative approach

suggested on p.322 of the paper (i.e. to use the coefficient of variation between clusters within each group as an upper limit for the coefficient of variation in matched pairs designs). After examining the distribution of the resulting coefficient of variation we selected 0.10 as the value for our subsequent power calculations since more than 90% of the data sets had values under that threshold.

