#### 9.4.2 ANALYSIS OF THE PRIMARY ENDPOINT(S)

We updated our analysis plan on 1.30.24 since two sites recruited only one participant. We wanted to make use of the data from their matched pairs rather than having to drop 4 sites from our analyses. Thus, to increase the efficiency of our matched pair design and maximize data utilization from all sites we will not account for the matching of clusters in our analyses.

We will test differences between treatment groups in the proportion of participants who are engaged and retained in treatment using generalized linear mixed models (GLMM). GLMM models will include a random effect for site to account for potential positive correlations among observations within sites and will evaluate the fixed effect for the interventions. For the PAM outcome, we plan to conduct linear mixed models, where the response variable will be the PAM score at the week-36 assessment and at 3-months post-partum. Models will include a random effect for site and will evaluate fixed effects for the interventions and baseline PAM scores. If assumptions of normality are violated, we will consider transformations or alternative distributions to determine the model with the best fit. Due to the small number of samples, we will use small sample corrections in our mixed models. For continuous outcomes we will use Satterthwaite's degrees of freedom approximation given the small number of clusters and high variability in size of clusters in our study. For binary outcomes we will use restricted pseudo-likelihood with between-within correction to the degrees-of-freedom.

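### The 80% power for retention in section 9.2 is not what its named formula (69-71%) or its named permutation test (about 50%) gives, and no power is stated for the mixed model that section 9.4.2 will run

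*Combined protocol and SAP*

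**What the plan says.** Section 9.2 describes the design as "We plan to recruit a sample of 6 matched pair clusters (total of 12 clusters), with 6 clusters per condition". The size given is 20 women in each cluster and 264 overall. The section says that "this sample size achieves 80% power to detect a clinically meaningful minimum difference of 0.20", with 0.94 retained under CC and 0.74 under ECHO. The test named there is for "differences between models of care in the proportion of women retained in treatment at delivery using a permutation test", at a two-sided type 1 error of 0.05. The method is the Hayes-Bennett approach for matched-pair cluster trials with a CV of 0.10.

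Section 5.5 explains the two site sizes: "132 in each treatment group with an average of 20 participants per site, allowing for 10% attrition". That is 264/12 = 22 enrolled per site, and 22 × 0.9 = 19.8, or about 20, after attrition.

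Section 9.4.2, updated on 1.30.24 because two sites had recruited one participant each, says "we will not account for the matching of clusters in our analyses". Retention is now tested with a generalized linear mixed model (GLMM) with a random site effect: "For binary outcomes we will use restricted pseudo-likelihood with between-within correction to the degrees-of-freedom". The section mentions no permutation test and states no power. Both sections are current text.

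**The concern.** Section 9.2 combines two different things: a permutation test on six pairs, and a power figure from a normal-approximation formula. With so few pairs the permutation test has very coarse p-values, which the formula does not see. Section 9.4.2 then adopts a third procedure, and section 9.2 was not revised to match.

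Retention is a primary outcome and the one used to justify 264 women. A reader of a non-significant result would set it against 80% power for a 20-point difference. Correcting only the number of women per site in the matched-pair formula would still describe a test that is no longer planned.

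**Working it through.** **Inputs.** Section 9.2 gives p1 = 0.94, p0 = 0.74, difference 0.20, CV = 0.10, c = 6 pairs and two-sided 0.05 (z = 1.96). Women per site, m, is 20 or 22 (sections 9.2 and 5.5). The value 40 is tried because the Patient Activation Measure calculation in section 9.2 still uses 40 per site.

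**Variance of one pair difference.** V = [p1(1−p1) + p0(1−p0)]/m + CV²(p1² + p0²) = (0.0564 + 0.1924)/m + 0.01 × (0.8836 + 0.5476) = 0.2488/m + 0.014312.

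- m = 20: V = 0.02675
- m = 22: V = 0.02562
- m = 40: V = 0.02053

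**The plan's own figure.** The matched-pair formula has power = Φ(√[(c−2) × 0.20²/V] − 1.96). The unmatched form uses c−1.

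| m | Matched (c−2 = 4) | Unmatched (c−1 = 5) |
|---|---|---|
| 20 | Φ(2.446 − 1.96) = 68.6% | Φ(2.734 − 1.96) = 78.1% |
| 22 | 70.5% | 79.8% |
| 40 | 79.7% | 87.7% |

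The named formula does not give 80% at 20 or 22 per site. At 20 per site it needs 7.25 pairs for 80%. Two variants come close to 80%: the matched formula at 40 per site, and the unmatched formula at 22.

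**The named test.** Randomization is within pairs (section 6.3), so six pairs give 2⁶ = 64 sign assignments. The smallest two-sided p-value is 2/64 = 0.031 and the next is 4/64 = 0.0625. The test is significant at 0.05 only if all six pair differences have the same sign. In the normal approximation, leaving out the negligible chance that all six favour ECHO, power = Φ(0.20/√V)⁶.

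- m = 20: Φ(0.20/0.1636)⁶ = 0.889⁶ = 49.5%
- m = 22: 51.1%
- m = 40: 60.1%
- m unlimited: SD = √0.014312 = 0.1196, so 0.953⁶ = 74.8%

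Simulation with beta site proportions gives 48.2% (m = 20), 50.4% (22), 58.6% (40) and 68.0% (10,000). Logit-normal proportions give 50.7%, 53.1%, 62.6% and 72.5%. Truncated-normal or uniform proportions give 38-42% at 20-22, partly because truncation shrinks the true difference to about 0.18.

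**Sensitivity of the ceiling to CV.** With unlimited women per site, the normal-approximation limit is 74.8% at CV 0.10, 82.5% at 0.09 and 99.8% at 0.05. It crosses 80% near CV 0.093. At 20 per site the test still has only 70% at CV 0.05, and just reaches 80% at CV 0.

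**The planned test.** This is a logistic GLMM with a random site effect, restricted pseudo-likelihood and 12 − 2 = 10 between-within degrees of freedom. The documents give only the two one-woman sites, so all other site sizes below are assumptions.

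| Between-site assumption | Equal sites of 20-22 | Two one-woman sites, about 264 women in total |
|---|---|---|
| CV 0.10 in each arm (beta, logit-normal or truncated normal) | about 67-76% | about 65-79% |
| Common logit SD 0.62 | 80.5-83.6% | 77.5-82.9% |
| Common logit SD 0.7 (not matched to CV 0.10) | 77-80% | 71-75% |

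In the first row, the lowest values count non-converged fits as non-significant. The most uneven pattern (1, 8, 15, 25, 35 and 48 women per arm, beta sites) gives 64.6% that way and 71.3% among converged fits. With one-woman sites and the other ten sites at 20, the range is 64-73%.

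The rows differ for a structural reason. A CV of 0.10 needs a logit-scale site SD of about 1.54 at 0.94 but about 0.39 at 0.74, whereas a model with one site variance assumes them equal. A common SD of 0.62 keeps about the same summed between-site variance but implies arm CVs of about 0.04 and 0.15.

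**The case against.** Several objections carry weight.

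- **CV 0.10 is described as conservative.** Section 9.2 treats it as an upper limit for a matched design. A reader might infer that the permutation test could not reach 80% at any number of women per site. The documents do not support that as a general statement: it holds at CV 0.10 in both arms, but not at about 0.09 or below. With a common logit SD of 0.62 the limit is 88%.
- **The planned model may have close to 80%.** A reader might infer that 65-79% is the GLMM's power. That range depends on assumed site sizes and on imposing the same CV in both arms. A common logit variance gives about 77-84%.
- **The 80% is not without any basis.** The unmatched formula gives 79.8% at 22 per site, and the analysis is now unmatched. But section 9.2 names the matched formula, and 22 per site makes no allowance for the 10% attrition. A reader might also suppose that 80% is left over from a design with 40 per site. The documents do not say where it came from.
- **Section 9.2 records how the trial was sized, and section 9.4.2 dates and explains its change.** That is fair, and a null result is better read from its confidence interval. It does not rescue the figure, which fails for the formula and test that section 9.2 itself names.

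**Conclusion.** The point holds. On the plan's own inputs, 80% is about 10-11 points above the named formula (68.6-70.5%) and about 30 points above the named permutation test (about 48-51%) at 20-22 women per site. The permutation figure assumes permutation within pairs, as the randomization implies, and CV 0.10 in each arm. At that CV the test stays below 80% with unlimited women per site, but this does not carry over to a CV of about 0.09 or lower.

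The test in section 9.4.2 has no stated power. A value under 80% is likely if CV is 0.10 in each arm, but it is not established, because the answer turns on the site sizes and on how between-site variation is specified. This is a defect in the stated justification. It does not show that the planned analysis is invalid.

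**What to change.** In section 9.2, remove the permutation test and the matched-pair formula as the basis of the 80%. State instead the power of the section 9.4.2 model for 0.94 vs 0.74: unmatched logistic GLMM, random site effect, restricted pseudo-likelihood and 10 between-within degrees of freedom, simulated at the actual site sizes, which the sponsor knows. Show results under both between-site assumptions (CV 0.10 in each arm, and a common logit-scale variance) over a range of CV, and say how non-converged fits are counted. Do not insert a fixed figure before that simulation is done; the ranges above are illustrative.

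If a permutation test is kept as a sensitivity analysis, say that it needs all six pairs to agree and has about 50% power at these site sizes and CV 0.10.

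The cost is a small simulation and a short rewrite of section 9.2. No extra patients are needed and the analysis does not change. The downside is that the stated power may be less favourable.

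### Section 9.2 justifies a coefficient of variation of 0.10 by saying more than 90% of simulated data sets fall below it; the simulation as described gives about 68%

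*Combined protocol and SAP*

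**What the plan says.** Section 9.2 reports that no empirical estimate of the CV could be found and describes a simulation in its place. "We generated 10,000 data sets with 6 clusters each", "with true proportions assumed uniformly distributed between 0.72 and 0.99", and in each set "coefficient of variation values were calculated based on formula (9) in the manuscript". That formula is cited but not written out. The plan then chose its value: "we selected 0.10 as the value for our subsequent power calculations since more than 90% of the data sets had values under that threshold".

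The section calls the approach conservative on a separate ground, which is "to use the coefficient of variation between clusters within each group as an upper limit for the coefficient of variation in matched pairs designs".

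The value feeds the main power statement. The design is 12 sites "with 6 clusters per condition and 20 patients per cluster for a total of 264 patients", and "this sample size achieves 80% power to detect a clinically meaningful minimum difference of 0.20", 0.94 under collaborative care against 0.74 under ECHO, "setting a two-sided type 1 error rate of 0.05". Section 9.2 uses the same 0.10 for the PAM calculation and for the table of minimum detectable differences.

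Section 9.4.2, updated on 1.30.24, says the analysis will no longer account for the matching of sites.

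**The concern.** The simulation is the only quantitative support for the CV, and the CV enters every power and detectable-difference figure in Section 9.2. The inputs are stated closely enough to repeat the exercise. They imply a population CV of 0.091, so a sample CV from only six sites should exceed 0.10 often, and a share above 90% below 0.10 is hard to believe.

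At stake is whether 0.10 carries the margin of safety that the text gives it. If it does not, someone interpreting a null result would take the trial to be better protected against between-site variation than was shown.

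**Working it through.** **Inputs (all Section 9.2 unless noted).** Six sites per arm; true proportions uniform on 0.72 to 0.99; CV 0.10; 0.94 versus 0.74; two-sided 5% level. Site size is 20 as stated, or 264/12 = 22. The two agree if 20 is the number left after the 10% attrition in Section 5.5 (22 × 0.9 = 19.8), so both are shown.

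**Step 1: CV of the stated distribution.** Mean = (0.72 + 0.99)/2 = 0.855. SD = 0.27/√12 = 0.0779. CV = 0.0779/0.855 = 0.091.

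**Step 2: the stated share.** Data sets of six proportions were drawn from the uniform distribution, and the CV computed under several readings of the unprinted formula.

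| CV estimator | Share below 0.10 |
|---|---|
| True proportions, SD (n−1)/mean | 68.0% |
| As above, true mean as denominator | 68.2% |
| True proportions, SD (n)/mean | 83.0% |
| Sampled proportions, 20 to 100 women per site, no correction (n−1) | 31–55% |
| Sampled proportions, binomial variance removed (n−1) | 66–67% |
| Sampled proportions, binomial variance removed (n) | 77–80% |
| Binomial variance subtracted from true proportions (n−1), 40 per site | 93.5% |
| Same, 44 / 22 / 20 per site | 92.3% / 99.0% / 99.4% |

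The 90th percentile of the CV for true proportions is 0.116 (n−1) or 0.106 (n). Chance does not explain the gap: with 10,000 data sets the standard error is √(0.68 × 0.32/10,000) = 0.005, and 300 repeats of the full run ranged from 66.5% to 69.3%.

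Only the last two rows exceed 90%. They remove sampling variance from proportions that have none, which biases the CV downwards.

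**Step 3: effect on power.** The plan prints no power formula. I assume the standard cluster form:

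V = [p₀(1−p₀) + p₁(1−p₁)]/m + k²(p₀² + p₁²)

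power = Φ(√[(c−a)(p₀−p₁)²/V] − 1.96)

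Here c = 6, a = 2 for the matched form and a = 1 for the unmatched form, k is the CV and m the site size. With 0.74 and 0.94, the binomial sum is 0.1924 + 0.0564 = 0.2488 and the sum of squares is 0.5476 + 0.8836 = 1.4312.

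*Reproducing the plan's 80%.* Matched, k = 0.10, m = 40: V = 0.00622 + 0.01431 = 0.02053, and power = Φ(√(0.16/0.02053) − 1.96) = 79.7%. At m = 20: V = 0.01244 + 0.01431 = 0.02675, and power = 68.6%. The unmatched form at m = 22 gives 79.8%.

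*Changing only the CV.* Matched, m = 20, k = 0.116: V = 0.01244 + 0.01926 = 0.03170, and power = Φ(√(0.16/0.03170) − 1.96) = 61.3%. In full:

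| CV | Matched, m = 20 / 22 | Unmatched, m = 20 / 22 |
|---|---|---|
| 0.09 | 73.2% / 75.3% | 82.2% / 84.0% |
| 0.10 | 68.6% / 70.5% | 78.1% / 79.8% |
| 0.116 | 61.3% / 62.9% | 70.9% / 72.5% |
| 0.12 | 59.5% / 61.0% | 69.1% / 70.7% |

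**The case against.** The strongest reply is that the CV formula cannot be seen. If it includes a binomial-variance term and was applied to the simulated proportions with 40 women per site, the share is 93.5% and the sentence reports what was computed. Section 9.2 still uses 40 per site for the PAM calculation, and the matched formula returns 80% at 40, so that history is plausible. This stands as a reason not to say that the authors misreported their result. It does not rescue the justification, because the subtraction is not valid for true proportions. Applied to sampled proportions, where it belongs, it gives 66–67% (77–80% with the n divisor).

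Second, 0.10 is an assumed planning value, lies above 0.091, and was offered as an upper limit for a matched-pair CV. The first two points stand. The third was fair for a matched analysis, but Section 9.4.2 has dropped matching. The between-site CV is now the relevant quantity itself, so that cushion is gone.

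Third, 0.116 is no better founded than 0.10. At a mean of 0.94 it implies a between-site SD of 0.109, so one SD above the mean is 1.05, an impossible proportion; 0.10 already gives 1.03. This stands, and it favours showing a range over substituting another single value.

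A reader might infer that the simulation has been shown to be irreproducible and that the trial's power rests on a wrong number. The documents support neither, because the formula is not printed and 0.10 is not itself contradicted.

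**Conclusion.** On the plain reading of Section 9.2, 0.10 is about the 68th percentile of the simulated CVs (the 83rd with the n divisor), so the stated reason for choosing it does not hold. The only route found to more than 90% uses a correction that does not suit true proportions. Either the percentage is wrong or it reflects a misapplied formula; the documents do not show which.

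The consequence is moderate. Holding the plan to its own 90% criterion (CV 0.116 in place of 0.10) lowers power by 7 to 8 points, to about 61–63% matched or 71–73% unmatched. If the CV were 0.09, power would instead be about 73–75% or 82–84%. These figures rest on the assumed cluster formula, equal site sizes and the stated 0.94 versus 0.74.

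The matched form already falls short of 80% at a CV of 0.10 with 20 to 22 women per site. That shortfall comes from site size. It is a separate issue and should not be charged to the CV.

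**What to change.** Rerun the simulation and amend Section 9.2 in three places.

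1. Print the CV formula, the SD divisor and any site size that enters it.
2. Correct the percentage to what the rerun gives, or remove it. The 68% and 0.116 found here should not be entered as the authors' result until the formula is confirmed.
3. Replace the single 80% statement with power over CV 0.09 to 0.12 at the current 20 to 22 women per site. Name the power formula, and say whether it is the matched or unmatched form, given Section 9.4.2.

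The section should also say that the upper-limit argument applied to the matched analysis and does not carry over to the unmatched one. The PAM calculation and the table of detectable differences, which share the 0.10, should refer to the same range.

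The cost is wording and a less favourable stated power. The design, data collection and analysis do not change.

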### 9.3 POPULATIONS FOR ANALYSES

Primary analyses will use an intention-to-treat analysis population. If missing data are a significant issue, we will use sensitivity analyses and/or multiple imputation methods, depending upon the nature of the missing data. Datasets for sensitivity analyses include per-protocol, complete cases, missing imputed as positive outcome (e.g. retained in treatment) and/or missing imputed as negative outcome (e.g. not retained in treatment). Multiply imputed data sets will be based upon multiple imputation methods that are appropriate for clustered data and the quantity, type (missing completely at random, missing at random, not missing at random), and pattern (monotone, or non-monotone) of missing data. Our safety analysis data sets will include all enrolled patients.

### 9.4 STATISTICAL ANALYSES

#### 9.4.1 GENERAL APPROACH

We will follow CONSORT guidelines, modified for cluster randomized trials, for reporting the trial ([www.consort-statement.org](http://www.consort-statement.org))(IR-5). Plans for data analysis will follow the major aims articulated above (IR-1) and the matched-pain cluster-randomized study design. We will examine the distribution of variables through descriptive statistics and graphical tools to verify that model assumptions are met to assess relationships between variables. Data analyses will use the intent-to-treat principle and we will attempt to follow all participants regardless of their retention to treatment. Dropouts (MD-3) and completers will be compared on baseline characteristics. Missingness (MD-2,4) will be examined for quantity, type (missing completely at random versus missing at random or not missing at random), and pattern (monotone, or non-monotone). If missing data are a significant issue, we will use sensitivity analyses (MD-4) and multiple

imputation methods that are appropriate for clustered data to fill in missing values in order to minimize bias, maximize available information and get accurate estimates of uncertainty. The possible impact of missing data on interpretation will be discussed in reports.

